**Nasobiliary Drain Assisted EUS-guided
Gastroenterostomies in Unresectable Malignant
Gastric Outlet Obstruction**

1. Background

Importance of gastric outlet obstruction in malignant disease

Gastric outlet obstruction (GOO) counts among the most severe adverse events presenting in malignant tumors located in the gastroduodenal junction. It usually presents with abdominal pain, nausea, vomiting and weight loss. Gastric cancer is its most frequent cause; it presents in 20-30% of stage IV gastric neoplasias (1). Restarting oral intake is a foremost priority in these patients. Due to their usually poor performance score and short life expectancy, the ideal procedure should be minimally invasive, present a low adverse event rate and have a low risk of recurrence.

Management options and adverse events

Traditional management consists in a gastroduodenal derivative surgery. Unfortunately, long hospital admissions, and relevant short term morbitidy were serious issues regarding this procedure, although it presents the lowest recurrence rates among proposed procedures (2).

The development of endoscopic stents have allowed endoscopic stent placement to be considered the currently first line treatment in these patients, reaching a clinical success in 90% of patients in selected centers (3). Nevertheless, endoscopic stent placements presents some relevant drawbacks. First of all, the clinical success rates in less selected centers is probably lower. Secondly, adverse events during follow-up are relatively frequent, especially recurrent GOO due to tumoral ingrowth or, less frequently, to stent migration. Recurrent GOO might present in up to 30% of patients (3). The high recurrence rate is specially relevant, as some recent studies report median survivals in advanced gastric cancer of 13 months (4) Thus, we should not only aim at restoring bowel transit, but to keep it functioning until the patient's death.

Novel endoscopic alternatives

The first endoscopic approach to achieve a functional gastrojejunostomy was through natural orifice transluminal endoscopic surgery (NOTES), where the peritoneal cavity is reached through the stomach. Once in the peritoneal cavity, a jejunal loop is clasped with a grasper and retrieved into the gastric cavity, suturing both hollow structures (5). Although prospective, proof of concept animal studies have shown its feasibility (6,7) and successful procedures in humans have been performed (8), it is a very demanding procedure even in highly skilled endoscopists. Endoscopic ultrasound guided gastroenterostomy (EUS-GE) is currently the preferred method to achieve an endoscopic gastric bypass in malignant GOO. An echoendoscope is used to identify the target bowel loop from the gastric cavity. To ease the identification of the target, different fluid solutions are injected into the bowel to distend it. Various methods have been proposed to reach this distention. In the endoscopy units taking part in the present study, the nasobiliary drain assisted EUS-GE is used, where a nasobiliary drain is advanced through the malignant stricture into the distal duodenum or the jejunum, and, once in place, liquids are pumped into the target bowel loop. Once the target bowel loop is identified, a lumen apposing metal stent (LAMS) is placed across both organs. After demonstrating its feasibility in animal studies (9,10), it has been extensively used in patients (11).

Available results of EUS-GE

Self-expandable metal stents (SEMS) achieve technical success in 97% of patients, with 87% achieving technical success, while a relevant proportion of patients present recurrent GOO, which presents approximately 3 months after deployment (12). A recent multicenter retrospective study comparing SEMS and EUS-GE observed similar proportions of technical and clinical success rates, while EUS-GE presented

lower rates of recurrent GOO and reintervention (13). Due to the low number of centers performing this procedure, the nasobiliary drain assisted EUS-GE has not yet been standardized, with significant differences among operators.

2. Objectives

Primary aim

- To describe different variants in the nasobiliary drain assisted EUS-GE technique, offering a detailed step by step description of the procedure performance by different endoscopists

Secondary aims

- To describe the proportions of technical and clinical success.
- To describe the adverse events encountered, their severity according to ASGE standards and their management.
- To describe the time elapsed between the procedure and the initial oral intake.
- To describe the evolution of the oral intake during the first month after the procedure
- To assess the impact of the operators experience on procedure times, adverse events and technical issues.
- To assess the impact of the procedure on the quality of life of the participating patients.

4. Design

Prospective, multicenter case-series

5. Methods

Study population

All consecutive patients over 18 years of age submitted to any of the participating center's endoscopy units to receive a nasobiliary drain assisted EUS-GE for unresectable malignant GOO are eligible to participate in this study.

Inclusion and exclusion criteria

Inclusion criteria:

- Unresectable malignant gastric outlet obstruction
- Scheduled placement of a nasobiliary drain assisted EUS-GE
- Age >18 years.

Exclusion criteria:

- Previous gastroduodenal surgery
- Previous endoscopic or surgical treatment for gastric outlet obstruction
- Simultaneous malignant biliary obstruction requiring endoscopic treatment
- Unable to understand the questionnaires
- Distal bowel obstruction
- Ascites grade 2 or superior
- Uncorrectable coagulation disorders (INR>1,5) or severe thrombocytopenia (<50000 platelets/mm3).

Definitions of the outcomes employed to assess primary and secondary variables

1. Technical success: Dichotomous variable. Defined as a correct placement of the LAMS, with one flange inside the gastric cavity and the other one in the small bowel. It should be confirmed endoscopically or fluoroscopically

2. Clinical success: Dichotomous variable. Defined as a GOOSS ≥ 2 . It will be assessed at days +7 and +30.
- 3.
4. Recurrent GOO: Dichotomous variable. In patients achieving clinical success in day +7, recurrent GOO is defined as the development of nausea and vomiting and/or a GOOSS < 2 .
5. Persistent GOO: Dichotomous variable. Continuing nausea, vomiting, and inability to tolerate PO intake up to or occurring within 2 weeks after the procedure.
6. Major complications: life-threatening or severe complications requiring treatment and/or hospitalization (The adverse event severity will be graded according to the ASGE lexicon).
 - a. Early major complications: complications occurring within 7 days after the intervention.
 - b. Late major complications: complications occurring 7 days or later after the intervention.
7. Minor complications: not life-threatening or moderate or severe complications that do not require hospital admission.
8. Reintervention: Dichotomous variable. Any procedure (endoscopic, radiologic or surgical aiming at treating a recurrent GOO, persistent GOO or any procedure related adverse event).
9. Gastric outlet obstruction score system: Presents the following categories 0 (*nil per os*), 1(liquids), 2(soft diet), 3 (full diet or low residue diet).
10. Target bowel loop diameter (mm): Diameter measured with the EUS of the dilated bowel loop. It should be measured just before placing the stent.

11. Total volume infused (ml): Volume of saline, methilene blue solution or radiopaque contrast solution instiled to dilate the target bowel loop (each one will be individually measured).

12. Balloon dilation: Dichotomous variable. At discretion of the endoscopist, after deploying the stent, it might be dilated with a controlled radial expansion balloon dilator.

Intervention

At inclusion

Informed consent will be obtained. A clinical interview and a physical examination will be performed. The European Organization for Research and Treatment of Cancer QoL Questionnaire Core 30 (EORTC-QLQ-C30), which includes 30 items covering a global health status scale, five functional scales and ten symptom scales will be assessed in a telephone interview.

Endoscopic procedure

All procedures will be performed under sedation. An assistant endoscopist or research nurse will retrieve all data regarding the procedure. Firstly, an upper digestive endoscopy is performed with a conventional gastroscope. A guidewire is passed through the malignant lesion causing the gastric outlet obstruction. Once the guidewire is located in the distal duodenum/proximal jejunum, a nasobiliary drain (Nasal Biliary Drainage Sets, Cook medical, Indiana) is advanced over the guidewire until its distal end is placed in the distal duodenum/jejunum. At this point the gastroscope is substituted by a therapeutic echoendoscope. With the echoendoscope in place, the target bowel loop is filled with saline combined with methilene blue and radiopaque contrast. The echoendoscope is used to identify the target bowel loop. After

identifying the target, a lumen apposing metal stent (Axios, Boston Scientific, Massachusetts) is deployed across the gastric and bowel using its electrocautery enhanced deployment device.

Post procedure

Oral liquid intake can be restarted 4h after the procedure in patients presenting no signs or symptoms suggesting any adverse event. Patients with an adequate tolerance might be discharged.

Follow-up

Clinical telephone interviews by an experienced research nurse will be held via telephone calls 1 day, 7 days and 30 days after the procedure. Oral intake and adverse events will be assessed every visit. Thirty days after the procedure a second evaluation of the EORTC-QLQ-C30 will be performed.

Sample size

Although EUS-GE is a rather infrequent procedure, we aim at including at least 5-10 procedures/endoscopist, in order to present each operator's *modus operandi*. Thus, recruitment will be active until a minimum of 5 procedures/endoscopist is reached or until a total sample size of 50 patients is reached, with at least 4 endoscopists including >5 procedures). To assess the secondary endpoint of the quality of life, previously published papers assessing QoL in patients with unresectable malignant GOO using the EORTC-QLQ-C30 reported mean global health status scores of 36.6 (SD: 20.1) and 45 (SD: 20.3) before treatment. To detect at least a 14-points change

with a 5% alfa risk and an 80% power, 33 subjects were estimated to be needed. Assuming a 20% of losses, 40 patients were required.

Adverse events monitoring

Adverse events (AE) are defined as any event preventing from completing the procedure, causing or lengthening a hospital admission or conditioning further interventions or unscheduled hospital or out-patient clinic visits. According to the time of diagnosis, they are classified as intraprocedure (diagnosed in the endoscopy unit during or immediately after the procedure), postprocedure (diagnosed in the 7 days following the procedure) or delayed (diagnosed beyond the first 7 days after the procedure). Causal relationship will be categorized into definitive (clearly related), probable (probably related), possible (might be related) or unlikely (there are other more likely causes). Severity will be assessed according to the ASGE recommendations

Consequence	Severity			
	Mild	Moderate	Severe	Fatal
Stop (or not even starting) a procedure	x			
Post-procedure out-patient visit	x			
Unplanned respiratory support during the procedure		x		
Unplanned hospital admission for 3 nights or less	x			
Unplanned hospital admission for 4-10 nights		x		
Unplanned hospital admission for 11 or more nights			x	
Intensive Care Unit admission for 1 night		x		
Intensive Care Unit admission for 2 or more nights			x	
Blood transfusion		x		
Endoscopic procedure		x		
Radiologic procedure		x		

	Severity			
Consequence	Mild	Moderate	Severe	Fatal
Surgical procedure			x	
Permanent disability			x	
Death				x

The principal investigator at each center is responsible of communicating all adverse events (all severe or fatal adverse events, regardless of the causal relationship and at least possible for moderate or mild events) to the principal investigator.

Data retrieval

Data were collected and managed using the SEED Research Electronic Data Capture tool (REDCap), a secure, web-based application created to support data capture for research studies providing semiautomatic data quality control (9). Patient-related and procedural data were included by the local investigators at stent deployment. Patients will be identified with a unique code. The database is password protected. Only the investigators have access to the database.

Local follow-up was performed according to each center's protocols. Regardless of the local follow-up, all patients underwent a centralized follow-up via telephone calls by an experienced research nurse, at inclusion, 1, 7 and 30 days after stent deployment. The EORTC-QLQ-C30 questionnaires were administered at the inclusion and at the 30 days telephone visits. Only in case the patient was admitted at the principal investigator center and preferred a personal interview, were the questionnaires administered in a face-to-face interview. Oral intake was evaluated 1, 7 and 30 days after the procedure.

6. Statistical analysis

Categorical variables were reported as percentages. Normally distributed continuous variables were reported as the mean with the standard deviation values. Non-normally distributed continuous variables were reported as the median and interquartile range. The EORTC QLQ-C30 descriptive analysis was performed with a specifically programmed Stata command (10). Variables regarding the procedure step by step analysis will only undergo a descriptive analysis. Differences between the different outcomes of the EORTC-QLQ-C30 will be assessed using linear mixed models with fixed effects for baseline values, and interaction with oncological treatment. The statistical analysis will be performed using the Stata package (StataCorp. 2013, College Station, Texas).

7. Ethics

Benefit risk assessment

Patients taking part in the study will not gain any personal benefit. We consider taking part in the study does not increase the risks associated to the procedure. The study is purely observational; data retrieval will not be performed by the operator. Thus, we consider the procedure in participating patients should defer from those EUS-GE performed in other patients. Follow-up will be performed via telephone calls, so the patient will not have to travel to take part. The procedure associated risk are well documented in the published literature, with an adverse event risk of 5%. The main risk is a hollow viscus perforation, followed by GI bleeding, and sedation associated procedures (aspiration pneumonia).

The study product, AXIOS™ (Boston Scientific) 20x10mm and 15x10mm lumen apposing metal stents, was originally designed to create internal drains for pancreatic fluid collections. Currently they are used in various other indications. Their deployment creating EUS-GE in patients presenting malignant unresectable GOO is increasing, both in Europe and in the United States, with various published case series.

8. Timeframe

First year

Recruitment of patients. Follow-up

Second year

Recruitment of patients. Follow-up (Recruitment will be active until the predetermined sample size of a minimum of 5 procedures/endoscopist is reached or until a total sample size of 50 patients is reached, with at least 4 endoscopists including >5 procedures).

Third year

Data análisis. Presentation in scientific meetings. Manuscript redaction.

9. Bibliography

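### Time to initial oral intake has no rule for patients who never resume, and under the general rule they would drop out and shorten the reported time

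*Combined protocol and SAP*

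**What the plan says.** Among the secondary aims in section 2 is "To describe the time elapsed between the procedure and the initial oral intake". Section 6 (Statistical analysis) does not mention this variable. Only two of its rules can apply: "Normally distributed continuous variables were reported as the mean with the standard deviation values" and "Non-normally distributed continuous variables were reported as the median and interquartile range". No Kaplan-Meier, cumulative incidence, censoring or competing-event method is named, and nothing is said about a patient without an intake time.

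The plan does foresee patients who may take nothing by mouth:

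- Persistent GOO (section 5, outcome definitions, item 5) is defined as "Continuing nausea, vomiting, and inability to tolerate PO intake up to or occurring within 2 weeks after the procedure".
- The obstruction score (item 9) has a category 0 for nothing by mouth.
- The adverse event definition covers events that stop the procedure from being completed.
- After the procedure, "Oral liquid intake can be restarted 4h after the procedure in patients presenting no signs or symptoms suggesting any adverse event", so early restart is conditional.

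On timing, the Data retrieval section says "Oral intake was evaluated 1, 7 and 30 days after the procedure". Item 3 of the outcome definitions is blank in the text available, so nothing here relies on a definition being absent from that list.

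**The concern.** A time to an event has no value in a patient in whom the event does not occur. If such a variable is summarised as an ordinary continuous measurement, those patients become missing and the summary describes only those who resumed. The patients lost are those with the worst result, so the error has one direction: the reported time can only be too short, never too long.

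The background in section 1 treats resuming oral intake as a leading priority for these patients, so readers are likely to cite this number. A median quoted without its denominator would look better than the experience of everyone in whom the procedure was started.

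**Working it through.** **Plan's own figure.** There is none to reproduce. The documents give no expected time, rate of non-resumption or precision for this outcome. The sample size calculation concerns quality of life only and has no bearing here.

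**Inputs.** Let q be the share of patients with no oral intake by day 30. It is an assumption, shown at 5%, 10% and 20%. For scale, the Sample size section sets recruitment to run until a minimum per endoscopist is met or "until a total sample size of 50 patients is reached, with at least 4 endoscopists including >5 procedures", so 50 is used as the total.

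**Formulas.** Rank non-resumers as longest. No distribution is needed.

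- The p-th quantile of all patients is the p/(1 − q) quantile of the resumers.
- Conversely, the p-th quantile reported from resumers alone is the p(1 − q) quantile of all patients.

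| q | All-patient median, as percentile of resumers | All-patient upper quartile, as percentile of resumers | Resumers-only median, as percentile of all | Resumers-only upper quartile, as percentile of all |
|---|---|---|---|---|
| 5% | 0.50/0.95 = 52.6 | 0.75/0.95 = 78.9 | 0.50 × 0.95 = 47.5 | 0.75 × 0.95 = 71.25 |
| 10% | 0.50/0.90 = 55.6 | 0.75/0.90 = 83.3 | 0.50 × 0.90 = 45.0 | 0.75 × 0.90 = 67.5 |
| 20% | 0.50/0.80 = 62.5 | 0.75/0.80 = 93.75 | 0.50 × 0.80 = 40.0 | 0.75 × 0.80 = 60.0 |

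At q = 25% the upper-quartile formula gives 0.75/0.75 = 1, the longest time among resumers. Above that the all-patient upper quartile is not reached, although a resumers-only summary would still print one. If anyone never resumes, the all-patient mean has no finite value.

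**In ranks.** With 50 patients and q = 10%, 5 have no value and 45 do. The resumers-only median is the 23rd ordered time, whereas half of all 50 have resumed at the 25th. The resumers-only upper quartile is about the 34th (0.75 × 45 = 33.75). Three quarters of all 50 have resumed at the 38th (0.75 × 50 = 37.5).

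**In time units.** This needs a distribution, which the documents do not give. If resumers' times are exponential (assumption), the all-patient value is the resumers-only value multiplied by:

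- median: ln[1/(1 − 0.5/(1 − q))]/ln 2 = 1.08, 1.17 and 1.42 for q = 5%, 10% and 20%;
- upper quartile: ln[1/(1 − 0.75/(1 − q))]/ln 4 = 1.12, 1.29 and 2.00.

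With lognormal times and a log-scale SD of 1 (assumption), the median factors are 1.07, 1.15 and 1.38. At q = 2%, one patient in 50, the median factor is 1.03 under either distribution. At q = 0 there is no bias.

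**The case against.** A reader might infer that the plan excludes patients who do not resume. It does not say so. Section 6 states a general rule, names no population for this variable, and does not forbid ranking non-resumers as longest or printing their number beside the median. That stands: the exclusion is what happens if the rule is applied as written with nothing added.

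A reader might also infer that every patient with persistent obstruction lacks a value. The documents do not support this. The aim concerns initial intake, not tolerated intake. Liquids may be restarted at 4 h when there are no signs of an adverse event, and persistent GOO is defined by inability to tolerate intake, which allows that intake was tried. A clinical failure, with a score below 2, may still be drinking at score 1. A technical failure may be followed by a reintervention and intake after that. If the event is first attempted intake, the group without a value narrows to those who take nothing at all in 30 days. This stands, and it is why the event must be defined.

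The rate may also be low. The only nearby figure, in section 1, is 97% technical success for metal stents, with similar success reported for EUS-GE. It measures a different thing, but at an illustrative q of 3% the median moves only to the 51.5th percentile of resumers (0.50/0.97) and the upper quartile to the 77.3rd (0.75/0.97). If many patients restart near 4 h, tied values could leave the median unchanged.

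Finally, failures stay visible elsewhere: technical success, clinical success at days 7 and 30, persistent GOO, and intake at days 1, 7 and 30. That limits the harm to the reader but does not correct this summary.

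**Conclusion.** The gap is real and minor. Under the only rule that can apply, a patient with no oral intake by day 30 would have no value, and the summary would be biased short. It does not follow that the reported time will be too short: that requires at least one such patient, and the documents give no rate.

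If 5% to 20% never resume (assumption), the shift in the median runs from slight to moderate. The upper quartile moves more, and its all-patient value may not exist at higher rates. The direction needs only that non-resumers count as longest; the sizes in time units also rest on the assumed distributions. The aim is descriptive, so no test, error rate or sample size is affected.

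**What to change.** Add a short rule to section 6:

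1. State whether the event is first attempted or first tolerated intake, and how its time is captured, since the scheduled assessments fall only on days 1, 7 and 30.
2. Keep every patient whose procedure was started in the denominator.
3. Report the number and percentage with no oral intake by day 30.
4. Give the median and upper quartile from the cumulative incidence of first intake to day 30, with death before intake as a competing event and loss to follow-up censored. If follow-up is complete, ranking non-resumers as longest gives the same quantiles and needs no special software.

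The cost is slightly more analysis and a slightly longer reported time. The upper quartile may have to be reported as not reached. No new contacts are needed, but if the time of first intake is not already recorded, a data field for it is.

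### Clinical success is defined by diet score alone, so a patient whose intake was restored by a further procedure can be counted as an EUS-GE success

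*Combined protocol and SAP*

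**What the plan says.** All references are to the combined protocol and SAP.

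- Section 2, secondary aims: "To describe the proportions of technical and clinical success".
- Section 5, definitions, item 2: "Clinical success: Dichotomous variable. Defined as a GOOSS ≥ 2 . It will be assessed at days +7 and +30". Item 9 of the same list shows that GOOSS grades diet level only, from 0 (nothing by mouth) to 3 (full or low-residue diet).
- Section 5, definitions, item 8, gives reintervention as a separate yes/no variable: "Any procedure (endoscopic, radiologic or surgical aiming at treating a recurrent GOO, persistent GOO or any procedure related adverse event". Technical success, recurrent GOO and persistent GOO (items 1, 4 and 5) are also separate yes/no variables.
- Section 5, adverse events monitoring: "Adverse events (AE) are defined as any event preventing from completing the procedure". The same sentence goes on to include events that lead to further interventions.
- Section 6 says that categorical variables are reported as percentages. It gives no rule for a patient who was reintervened before an assessment.

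**The concern.** The Background sets the goal in these terms: "we should not only aim at restoring bowel transit, but to keep it functioning". A success rate for EUS-GE should therefore describe intake that the EUS-GE itself restored and maintained. A definition that looks only at diet on the day of the call cannot separate that from intake restored by a second procedure.

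Reintervention will be reported as a percentage of its own, but two separate percentages do not show how many retreated patients are among the successes. A reader comparing this series with others could credit EUS-GE with results that belong partly to a rescue procedure.

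**Working it through.** **Does any rule exclude reintervened patients?** Setting the definitions side by side:

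1. Clinical success needs GOOSS of at least 2 and carries no other condition.
2. Recurrent GOO is counted among day-7 successes, but nothing says that it cancels a day-30 success.
3. Persistent GOO covers the first 2 weeks, but nothing says that it cancels success at either visit.
4. Reintervention is not linked to success, and success is not made to depend on technical success.

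The gap remains whether days 7 and 30 are reported separately or both are required. A patient retreated before day 7 can satisfy both assessments. So can one who succeeds at day 7, recurs, is retreated and is on soft diet at day 30.

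**The failed-stent route.** Inclusion rests on a scheduled procedure, so failed attempts are in the study. An event that prevents completion is an adverse event, and a procedure to treat a procedure-related adverse event is a reintervention. Such a patient is a technical failure but can meet the clinical success definition. This route is open only if clinical success is calculated over all attempted patients. If it is calculated over technical successes, these patients never enter the proportion. The plan does not say which.

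**Size.** The plan states no target rate, power or sample size for clinical success, so there is no figure of its own to reproduce. The inputs are n=50 (the recruitment total in the sample size section) and n=40 (the quality-of-life requirement in the same section).

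Effect of recoding one patient = 100/n: 100/50 = 2.0 points; 100/40 = 2.5 points.

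For illustration, take a plain rate of 90%. Section 1 gives this for enteral stents ("reaching a clinical success in 90% of patients in selected centers") and says that a retrospective comparison with EUS-GE "observed similar proportions of technical and clinical success rates". Let k be the number of counted successes who had been salvaged. The documents give no value for k; 0 to 3 is an assumption. Rate = (successes − k)/n, with exact (Clopper-Pearson) 95% intervals:

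| k | n=50 | n=40 |
|---|---|---|
| 0 | 45/50 = 90% (78.2–96.7) | 36/40 = 90% (76.3–97.2) |
| 1 | 44/50 = 88% (75.7–95.5) | 35/40 = 87.5% (73.2–95.8) |
| 2 | 43/50 = 86% (73.3–94.2) | 34/40 = 85% (70.2–94.3) |
| 3 | 42/50 = 84% (70.9–92.8) | 33/40 = 82.5% (67.2–92.7) |

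**The case against.** **Much of the information is already planned, and this largely stands.** Events leading to further interventions are adverse events. They are classed as intraprocedure, within 7 days or beyond 7 days, and graded partly by whether the consequence was endoscopic, radiologic or surgical. Describing their management is a secondary aim. A reader might infer that the timing and reason of reinterventions are not collected; the documents do not support that. What is missing is narrower. The class dates the diagnosis and not the procedure that treated it, and the planned analysis does not include a cross-tabulation of success by reintervention.

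**Separate components are a legitimate choice in a case series.** Loss and persistence of function have their own variables, and GOOSS regardless of later procedures is a valid description. That stands as a reason to keep plain GOOSS in the report. It does not make plain GOOSS a measure of what EUS-GE alone achieved.

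**The count is probably small.** Section 1 places recurrence after enteral stents at about 3 months, beyond the 30-day follow-up, and reports less recurrence and reintervention with EUS-GE. Section 7 cites an adverse event risk of 5%: 0.05 × 50 = 2.5 patients, or 0.05 × 40 = 2. Salvaged successes would be only some of these, so k=3 exceeds the number of all adverse events expected at that risk, although that figure may rest on another definition. At k=1 the intervals nearly coincide. This stands and keeps the point minor.

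**Conclusion.** The definition as written allows success to be credited to EUS-GE when another procedure restored intake. On a fixed denominator the rate is raised or unchanged, by 2 points per such patient at n=50 and 2.5 at n=40. This rests on the readable text: item 3 of the definitions list is blank in the extracted text, and whether it held anything relevant is unknown.

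Four stronger readings are not supported:

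- A reader might infer that the reported rate will be materially inflated. The documents give no count of salvaged patients, and it may be zero.
- A reader might infer that technical failures will be counted as clinical successes. That needs a denominator of all attempted patients, which the plan does not state.
- A reader might infer that a test or the sample size is affected. The endpoint is secondary and descriptive, and the only powered figure (33 subjects, 40 with losses) concerns quality of life.
- A reader might infer that patients who already had GOOSS 2–3 at entry will inflate the rate unseen. Eligibility sets no GOOSS limit, but at inclusion "A clinical interview and a physical examination will be performed", the follow-up section has oral intake assessed at every visit, and the data retrieval section lists a call at inclusion. Baseline GOOSS may therefore be covered. The data retrieval section names only days 1, 7 and 30 for oral intake, so this deserves a separate clarification and forms no part of this point.

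**What to change.** 1. At each of days 7 and 30, report clinical success as GOOSS of at least 2 with no earlier reintervention to restore the gastric outlet, whether for persistent GOO, recurrent GOO or salvage of a failed or misplaced stent.
2. State the denominator as all included patients with an attempted procedure.
3. Report plain GOOSS of at least 2 beside it, on the same denominator, so that the overlap with reintervention is visible and comparison with other series remains possible.
4. Record the date of each reintervention, so that it can be placed before or after each assessment.

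The cost is a change of wording, one date field and one extra line in the results table. The downside is a slightly lower reported success rate. Sample size and visit schedule do not change.
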